3.2 Favipiravir: The study drug

At the time of writing, definitive therapies for established COVID-19 remain to be defined. Significant interest exists in repurposing existing antiviral agents for use against COVID-19. Favipiravir is a purine nucleoside analogue, which acts as a competitive inhibitor of RNA-dependent RNA polymerase [8-10]. It has activity against influenza A and B including activity against oseltamivir and zanamivir-resistant influenza viruses, several agents of viral hemorrhagic fever, and SARS-CoV-2 in vitro [11-13]. Favipiravir is approved for novel epidemic influenza strains unresponsive to standard antiviral therapies in Japan [14].

Favipiravir was identified to have activity in vitro against SARS-CoV-2, albeit a high concentration was required as compared to chloroquine or remdesivir ($EC_{50} = 61.88 \mu M$) [15]. Despite a similarly elevated EC_{50} identified for favipiravir and Ebola virus, it was identified in 14 previous animal models to be highly effective as post-exposure prophylaxis for mice exposed to an Ebola virus challenges, with rapid virologic response preventing mortality [16-18]. Based on the dosing strategies and pharmacokinetic data from human influenza trials, an intensified dosing strategy of 6000 mg loading on day 1 followed by 1200 mg

PO BID maintenance therapy for 10 days was employed in a single-arm clinical trial for Ebola virus disease in Guinea [19].

In a retrospective analysis of 124 patients with Ebola virus disease in Sierra Leone, those treated with favipiravir had a significantly higher survival rate compared to patients receiving supportive management (56% v. 35.3%, p=0.027) [20]. Patients received favipiravir 800 mg PO BID on day 1 and 600 mg PO BID for days 3-11. Viral loads were quantified for 35 patients twice during their hospitalization and were significantly reduced amongst patients receiving favipiravir.

Favipiravir has also been used as pharmacologic post-exposure prophylaxis for Ebola virus disease [21]. In a case series of four healthcare workers with higher risk Ebola virus exposures, including two hollow-bore needle stick injuries, none of the patients who received 10 days of high-dose favipiravir developed Ebola virus disease.

Early clinical experience with favipiravir for COVID-19 is promising. An open-label nonrandomized trial of 80 patients with COVID-19 in China identified a significant reduction in the time to SARS-CoV-2 viral clearance in patients treated with favipiravir compared to historical controls treated with lopinavir/ritonavir [6]. Patients with mild or moderate COVID-19 were enrolled within 7 days from disease onset; those with severe or critical disease, ≥ 75 years old, chronic liver disease, or end-stage renal disease were excluded. Patients in the intervention arm received Favipiravir 1600 mg PO BID on day 1 followed by 600 mg PO BID on days 2-14. Both arms were co-treated with inhaled IFN- α 1b 60 μ g BID and therapy was continued until viral clearance, up to a maximum of 14 days. Thirty-five patients were assigned to favipiravir and 45 patients to lopinavir/ritonavir, with a median age of 47 (IQR 35.8-61); 13.7% were ≥ 65 years old. There was a significant reduction in the median time to viral clearance with favipiravir (4 days; IQR 2.5-9) as compared to lopinavir/ritonavir (11 days; IQR 8-13; p<0.001). Further, by day 14, 91.4% of patients in the favipiravir arm had radiographic improvement versus 62.2% of the lopinavir/ritonavir arm. There was a significantly lower rate of adverse events in patients receiving favipiravir (11.4% v. 55.6%, p<0.01).

In an open-label randomized trial in China, 240 patients with confirmed COVID-19 were randomized to favipiravir or arbidol [7]. Favipiravir was given at 1600 mg PO twice on day 1 followed by 600 mg PO BID until day 7-10. The clinical recovery rate by day 7 of treatment was higher amongst patients receiving favipiravir, albeit not achieving statistical significance (61.21% v. 51.67%, p=0.1396). Amongst patients with moderately severe disease, there was a significantly higher rate of clinical recovery by day 7 with favipiravir (71.43% v. 55.86%).

Top-line results are also available from an open-label, randomized, multicenter clinical trial recently conducted in 150 patients in India. Patients in the intervention arm received 1800 mg of Favipiravir PO twice daily on day 1 followed by 800 mg twice daily for up to a maximum of 14 days, along with standard supportive care. Randomization was stratified based on disease severity into mild (90 patients) and moderate (60 patients). The median time to cessation of oral viral shedding was 28.6% faster in the intervention arm although the difference was not statistically significant (Hazard Ratio 1.367 [95%CI 0.944,1.979]; p=0.129). Patients receiving favipiravir were reported to achieve clinical cure faster than controls and disease progression was delayed. No serious adverse events or deaths were reported in the intervention arm. Full study results have not yet been published.

In the current pandemic crisis, medical professionals are understandably focused more on stabilizing the very sick. However, if Favipiravir could work in any way to halt or prevent infection in the less sick (or even in the uninfected), it would be monumental in terms of returning to normal life. Because the drug has few side effects, taking Favipiravir prophylactically might help to prevent COVID-19 spreading. Even

if this treatment does not completely eradicate infection, Favipiravir treatment may help to decrease viral load, thereby allowing the host immune system to better combat the disease.

3.3 Favipiravir: Risk/Benefit Assessment

As of August 2020, more than 40 clinical studies with favipiravir have been conducted globally, mainly in the US and Japan. Favipiravir has been well tolerated in studies in adults and elderly subjects with uncomplicated influenza [22]. A consistent safety profile composed of relatively low frequencies of mild to moderate adverse events clustering around the system organ classes of gastrointestinal disorders has been characterized. Mild to moderate transient, asymptomatic elevations in serum uric acid and mild to moderate diarrhea are the two most common adverse events known to occur with favipiravir [2]. Favipiravir has been safely studied with therapy durations up to 22 days (JP120, Phase 1 study).

Favipiravir is considered a safe drug. No related serious adverse events occurred in licensure studies of favipiravir [23]. Preclinical and animal studies show no direct suppression of white blood cell types or immunosuppression by favipiravir. Genotoxicity studies indicate that favipiravir does not pose a clinical genotoxic risk; however, based on the results of embryo-fetal toxicity studies, favipiravir is not recommended for use in pregnant females, those who may become pregnant, or those who are nursing. Though an inhibitor of CYP 2C8 and aldehyde oxidase, few drugs are contra-indicated. Overall, the safety of favipiravir suggests that the potential benefit to human subjects exposed to a confirmed case of COVID-19 generally outweighs potential risks.

4.0 OBJECTIVES AND ENDPOINTS

The primary effectiveness objective of this study is demonstrating that treatment with favipiravir for COVID-19 patients with mild to moderate symptoms will shorten the time to sustained clinical recovery from study day 1 onward ('clinical endpoint component') compared to placebo.

The primary virologic objective (the secondary objective of the study) of the viral shedding sub-study is to demonstrate that treatment with favipiravir treatment will shorten the period of viral shedding ('viral shedding component') compared to placebo from study day 1 onward.

Demonstrate that treatment with favipiravir will reduce the proportion of subjects with COVID-19 related hospitalizations or emergency department visits compared to placebo from study day 1 onward.

Demonstrate that treatment with favipiravir will reduce the proportion of subjects with COVID-19 related hospitalizations or emergency department visits or the development from study day 1 onward of two or more new COVID-19 related symptoms compared to placebo from study day 1 onward.

Primary Efficacy Endpoint:

Time to Sustained Clinical Recovery defined as number of days from start of study treatment to Sustained Alleviation of Symptoms. The endpoint will be considered to have been met at the earliest time point from study day 1 onward at which the subject has reached Sustained Alleviation of Symptoms as defined by:

- (1) Blood oxygen saturation $\geq 94\%$ on room air at rest
- (2) Oral temperature $< 38.0^{\circ}\text{C}$ AND
- (3) All COVID-19 associated symptoms (stuffy or runny nose, feeling hot or feverish, chills or shivering, cough, sore throat, lack of energy or tiredness, nausea, headache, muscle or body aches, shortness of

breath, vomiting, diarrhea) (Symptoms related to smell or taste are not included in the primary endpoint) reported by the patient have reached a severity of “0 – none” or “1 – mild” in assessments for 4-point scale assessments

To meet the primary endpoint, criteria 1 through 3 (above) should be met and the subject is not known to have redeveloped any COVID-19 associated signs and symptoms (not including reduced sense of taste or smell) at a severity beyond mild for 4 consecutive days (inclusive of the day when clinical recovery was achieved) assessed from the start of study treatment to day 28, and subjects must survive with no hospitalization to day 28. The time from start of study treatment to the earliest time point that one through three (above) are met will be considered for the primary efficacy endpoint. For example, if clinical recovery was reached on study day 5 and sustained over study days 6, 7, and 8, the time of reaching the endpoint will be study day 5.

The subject will assess and score the severity of each COVID-19 associated symptom on a 4-point scale (for all symptoms besides vomiting and diarrhea: 0= none, 1= mild, 2=moderate, 3=severe. For vomiting and diarrhea: 0 = not at all, 1 = 1-2 times, 2 = 3-4 times, 3 = 5 or more times). The patient's blood oxygen saturation and severity of COVID-19 associated symptoms will be evaluated and reported once daily, preferably at or around the same clock time, by the subject (for a period of 10 days or longer in case that the subject does not achieve the primary endpoint within the first 10 days).

Beyond Study Day 10, once the subject meets the primary efficacy endpoint, the subject is not required to continue the self-assessment and reporting of COVID-19 symptoms. However, the study team, during all the in-person and remote patient visits will evaluate and report the severity of each of the COVID-19 associated symptoms and vitals as per the set frequency mentioned in the *Schedule of Activities*, under study staff responsibility.

Subjects who develop new COVID-19 symptoms post-randomization will be counted towards the primary outcome. The definition of the primary endpoint for such subjects will be identical to the definition used for any other subjects. To have the endpoint, all symptoms (those existing at enrollment and those appearing post-enrollment, not including symptoms related to smell or taste) will have to be no worse than 1 - mild, regardless of whether they existed at randomization or not.

For any subject who has incompletely submitted relevant data to assess clinical recovery, the primary endpoint is met on the first day from study day 1 onward where clinical recovery is reached, defined as none of the symptoms is worse than mild, as well as temperature $<38.0^{\circ}\text{C}$ and O2 saturation $\geq 94\%$, and considered sustained over the 3 following days when there is no known flare up of symptoms beyond mild. During the 3-day sustainability period, complete COVID symptom data (not including taste, smell) is required for at least 2 of the 3 days (COVID-19 symptom data can be missing for 1 of the first two sustainability days but not for the last day of sustainability). Missing information for temperature or O2 saturation during the 3-day sustainability period will not invalidate reaching the endpoint.

For any subject who has been lost to follow-up prior to Day 28, the investigators will make reasonable efforts to determine whether the subject has been admitted to the hospital or died up to Day 28. For subjects who experienced sustained clinical recovery prior to Day 28 and lost to follow-up, should the investigator be able to confirm no admission to the hospital and no death, the subject will be flagged as having the endpoint of sustained clinical recovery. Subjects who were lost to follow-up and for whom the investigator could not confirm lack of admission to the hospital or death before Day 28, will be flagged as the worst possible outcome regardless of clinical recovery.

Secondary Endpoints:**Key Secondary Efficacy Endpoint:**

- Proportion of subjects with COVID-19 progression, where progression is defined as the occurrence from study day 1 onward of any emergency department (ED) visit for COVID-19 worsening or shortness of breath **OR** hospitalization for COVID-19 worsening or shortness of breath **OR** death (narrow progression)
- Proportion of subjects with COVID-19 progression, defined as the occurrence from study day 1 onward of any ED visit for COVID worsening or shortness of breath **OR** hospitalization for COVID worsening or shortness of breath **OR** death **OR** the development of symptomatic worsening from study day 1 onward (defined as ≥ 2 additional COVID symptoms at a level of moderate or severe which have not existed at baseline or fever (temperature of $\geq 38.0^{\circ}\text{C}$) which has not existed at baseline or oxygen desaturation (O₂ saturation $<94\%$) which has not existed at baseline) (broad progression).

Viral Shedding Sub-Study:

- Time (number of days) to negative conversion (defined as undetectable viral load) of detectable SARS-CoV-2 viral RNA in RT-PCR assays of saliva, from start of study treatment to date of last viral assessment. Included: all subjects with a positive PCR on study day 1 or 2 or 3. The endpoint will be evaluated from study day 1 onward.

Additional Secondary Efficacy Endpoints

- Time (number of days) to negative conversion of positive SARS-CoV-2 viral culture assays of saliva, from start of study treatment to date of last viral assessment. Subjects with a positive saliva SARS-CoV-2 PCR on any study day will have viral cultures performed. Subjects with a positive viral culture on study day 1 or 2 or 3 will be included in this analysis. The endpoint will be evaluated from study day 1 onward.

Exploratory Endpoints (details of the planned analyses are described in SAP 3.1):

- Proportion of subjects showing sustained clinical recovery by study Day 1, 3, 5, 7, 10, 14, 21.
- Proportion of subjects showing resolution of Symptoms by Days 1, 3, 5, 7, 10, 14, 21, where resolution is defined as symptom severity of 0 for all symptoms as well as temperature of $<38.0^{\circ}\text{C}$ as well as oxygen saturation of $\geq 94\%$.
- Proportion of patients showing negative conversion of detectable SARS-CoV-2 viral RNA in saliva on study day 1 or 2 or 3 to undetectable viral load on Study Days 3, 5, 7, and 10. Included: all subjects with a positive PCR on study day 1 or 2 or 3.
- Proportion of patients showing negative conversion of positive SARS-CoV-2 viral culture in saliva on Study Days 3, 5, 7 and 10. Subjects with a positive saliva SARS-CoV-2 PCR on any study day

will have viral cultures performed. Subjects with a positive viral culture on day 1 or 2 or 3 will be included in this analysis.

- Proportion of subjects dying from any cause over an assessment period from start of study treatment until Day 28.
- Proportion of subject with COVID-19 progression, where progression is defined as the occurrence at any point from study day 1 to study day 28 of emergency department (ED) visit for any reason OR hospitalization for any reason.
- Proportion of subjects requiring mechanical ventilation over an assessment period from start of study treatment until Day 28.
- Time (number of days) to negative conversion (defined as viral load <100 copies) of detectable SARS-CoV-2 viral RNA (defined as viral load >100 copies) in RT-PCR assays of saliva, from start of study treatment to date of last viral assessment. Included: all subjects with a positive PCR on study day 1 or 2 or 3. The endpoint will be assessed from study day 3 onward.
- Time to Sustained Clinical Recovery defined as number of days from start of study treatment to Sustained Alleviation of Symptoms, evaluated from study day 3 onward.
- Proportion of subjects with COVID-19 progression, where progression is defined as the occurrence from study day 3 onward of any emergency department (ED) visit for COVID-19 worsening or shortness of breath OR hospitalization for COVID-19 worsening or shortness of breath OR death (narrow progression)
- Proportion of subjects with COVID-19 progression, defined as the occurrence from study day 3 onward of any ED visit for COVID worsening or shortness of breath OR hospitalization for COVID worsening or shortness of breath OR death OR the development of symptomatic worsening from study day 3 onward (defined as >2 additional COVID symptoms at a level of moderate or severe which have not existed (at any level of severity) at baseline or fever (temperature of $\geq 38.0^{\circ}\text{C}$) which has not existed at baseline or oxygen desaturation (O2 saturation <94%) which has not existed at baseline) (Broad progression).

Safety Endpoint:

1. Number (and proportion) of patients reporting treatment emergent adverse events (TEAEs) (by MedDRA system organ class and preferred term). See additional information on assessing adverse events under section 9.4.
2. Number (and proportion) of patients reporting serious treatment emergent adverse events (TEAEs) (by MedDRA system organ class and preferred term).
3. Vital Signs including oral temperature, heart rate, oxygen saturation with height and weight.
4. Clinical laboratory tests including Biomarkers, Chemistry, Coagulation and Hematology.

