5.0 STUDY DESIGN

5.1 Overall Design

This is a double-blinded, randomized, placebo-controlled, superiority trial of approximately 1250 adult outpatients with mild to moderate symptoms of COVID-19 not requiring hospitalization. Depending on the site of enrollment, subjects will be identified at COVID-19 testing centers, testing laboratories, or other clinical care settings. As this study will enroll outpatients only, to prevent violating quarantine requirements and decrease risk of COVID-19 for study team members, most study interactions will be performed remotely with no need for study subjects to leave their homes to fulfill their study obligations. Besides study visits on Day 1 and Day 10, which will be in-person, all other study interactions will be done remotely, using telehealth and video conferencing. Study materials will be provided to subjects at their home or in-site.

Subjects in the treatment arm (n= 625) will receive favipiravir orally taken approximately every 12 hours in addition to current standard of care treatment. The first two doses of favipiravir will be 1800 milligrams. The following doses will be 800 milligrams for a total of 10 days of therapy. Those in the control group (n= 625) will receive placebo orally, using the same numbers of tablets on day 1 and the subsequent 9 more days (total 10 days of treatment), in addition to current standard of care treatment. Saliva PCR testing will be performed at an accredited central laboratory. The site's Principal Investigators will be responsible for study recruitment and engaged as deemed necessary by the Study Team to ensure identification and reporting of maximum number of positive cases and prompt subject engagement/enrollment. This study will be listed at www.clinicaltrials.gov.

Subjects who provide informed consent, meet all inclusion and no exclusion criteria will be randomized on Treatment Day 1 in a 1:1 ratio to either the Treatment Group or the Control Group, in accordance with a computer-generated schedule prepared by a biostatistician. The randomization schedule will be incorporated into the Interactive Web Randomization System (IWRS). Randomization will then be performed by study personnel directly in the IWRS system. Study personnel will be instructed not to randomize until subject has been confirmed to meet all inclusion/exclusion criteria on treatment Day 1.

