7.1.3 Dosing and Administration

Subjects will be randomly assigned to favipiravir (the first two doses are 1800mg given approximately 12 hours apart and followed by 800mg approximately every 12 hours to treatment day 10) or identically dosed placebo in 200 mg tablets. All tablets will be supplied in a bottle.

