7.7.3 Specimen Collection Days

Saliva Specimens will be collected by the subject at Study Days 1 to 10. Care will be taken to ensure that sampling methods are consistent for each individual subject across all included timepoints, to limit any

bias due to potential differences in viral load. The first collection of saliva samples will be observed by a Study Team member during Day 1 in-person visit.

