9.2 Study Procedures

9.2.1 Screening, Baseline, Randomization and Treatment (Day 1)

The following procedures will be performed at the Day 1 in-person visit:

- Confirmation of positive SARS-CoV-2 test result
- Confirm subject meets all inclusion and none of the exclusion criteria
- Review the study with the subject and obtain written informed consent and Health Insurance Portability and Accountability Act of 1996 (HIPAA) authorization, or equivalent in another respective country, as applicable such as *Lei Geral de Proteção de Dados Pessoais (LGPD)* in Brazil
- Register the subject in IWRS to allot a unique subject ID (screening number)
- Randomize subject to treatment arm in IWRS as per randomization schedule
- IWRS to assign unique randomization number to the subject
- IWRS to assign IP kit number as per randomization schedule
- Record demographics (age, race, ethnicity, gender)
- Review and record medical history, surgical history
- Review and record smoking, alcohol and medication history
- Document all current medications, including medications over the counter and herbal medications
- Record height and weight
- Record COVID-19 symptoms for inclusion
- Record confirmation of positive SARS-CoV-2 test result
- Record number of days since onset of symptoms
- Collect blood sample for below listed blood tests:
 - CBC with differential, Electrolytes, BUN, Creatinine, Random Blood Serum Glucose, AST, ALT, Bilirubin, uric acid, SARS-CoV2 IgG, IL-6, IL-10, ESR, CRP, D-Dimer, ferritin. (CRP = C-reactive protein, IL-6 = Interleukin-6, IL-10 = Interleukin-10, CBC = Complete Blood Count).
 - Site do not require to wait for blood test result to randomize subjects.

- Provide the allotted IP kit, the blinded treatment (either favipiravir or placebo), and other study materials to the subject
- Assist the subject in downloading the ePRO app, create ePRO credentials for the subject, train the subject on how to use the ePRO and enter the Day 1 Dose 1 visit data with the subject during the visit to ensure the subject's understanding.
- Until the sub-study enrollment is completed (112 events have been counted), all subjects will be enrolled into the viral shedding sub-study. However, if they choose so, subjects can opt-out of participating in the viral shedding sub-study.

9.2.2 Treatment Day 1 to Day 10

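### The viral-shedding set admits subjects on Day 2 or Day 3 PCR results, after dosing has begun, so an effective drug can change who is analysed

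*Combined protocol and SAP*

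**What the plan says.** Protocol Section 4.0, under the viral shedding sub-study, sets the analysis population for time to undetectable saliva RNA: "Included: all subjects with a positive PCR on study day 1 or 2 or 3". The synopsis repeats the rule. The culture endpoint has a parallel one: "Subjects with a positive viral culture on study day 1 or 2 or 3 will be included in this analysis". Both endpoints count time from the start of study treatment, and "The endpoint will be evaluated from study day 1 onward".

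Section 5.1 says that eligible subjects "will be randomized on Treatment Day 1 in a 1:1 ratio to either the Treatment Group or the Control Group". Dosing starts the same day: Section 9.2.1 has staff help to "enter the Day 1 Dose 1 visit data with the subject during the visit", and in Section 7.1.3 "the first two doses are 1800mg given approximately 12 hours apart". Saliva is collected daily on Days 1 to 10. Section 7.7.3 adds that "The first collection of saliva samples will be observed by a Study Team member during Day 1 in-person visit", but no section says that this sample comes before the first dose.

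The analysis populations in Section 10.3 include none restricted to subjects who are saliva-positive at baseline. Section 10.8.5 names one sensitivity analysis, on relapse after recovery, and refers the full list to SAP 3.1, whose text is not in the document reviewed.

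**The concern.** An analysis set should be fixed by information that treatment cannot influence. Day 2 and Day 3 PCR results come after randomisation and after at least one dose, and Section 3.2 expects the drug to lower viral load, which is the quantity that decides entry. Two things follow for subjects not positive on Day 1.

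- **Selection.** If the drug works, fewer of them turn positive on favipiravir, so fewer enter from that arm.
- **Built-in event-free time.** Someone first positive on Day 2 or 3 cannot convert before then, yet the clock started at first dose. If such subjects are more common on placebo, event-free time is unequal between arms. Likewise, in the exploratory Day 3 conversion proportion a subject first positive on Day 3 is in the denominator but cannot count as converted that day.

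Such subjects can be expected. Section 6.1 accepts RT-PCR or rapid antigen on several specimen types, collected up to 72 hours before randomisation, so an eligible subject can be saliva-negative on Day 1. At stake is whether the viral estimate reads as a comparison of randomised groups.

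**Working it through.** **1. The plan's own figure.** Section 10.2.4 gives 112 events for HR 1.7, 80% power and two-sided alpha 0.05. Schoenfeld's formula with 1:1 allocation:

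events = 4 × (1.960 + 0.842)² / (ln 1.7)² = 31.4 / 0.2816 = 111.5, rounded up to 112.

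The figure reproduces (power at 112 events is 80.2%). It does not depend on how positivity is defined, so changing the set leaves it at 112.

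**2. Share of late entrants.** Let p be the proportion saliva-positive on Day 1 and e the proportion of the others who turn positive on Day 2 or 3. The late-entrant share of the set is (1 − p)e / [p + (1 − p)e].

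The documents give neither p nor e. The nearest figure is the 94.1% sensitivity of saliva against nasopharyngeal swab in Section 7.7.7. It is not a Day 1 rate, because the qualifying test may be three days old. Assume e = 0.50 on placebo and 0.20 to 0.35 on favipiravir:

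| p | Placebo | Favipiravir |
|---|---|---|
| 0.94 | 0.03/0.97 = 3% | 0.012/0.952 to 0.021/0.961 = 1-2% |
| 0.80 | 0.10/0.90 = 11% | 0.04/0.84 to 0.07/0.87 = 5-8% |
| 0.60 | 0.20/0.80 = 25% | 0.08/0.68 to 0.14/0.74 = 12-19% |

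**3. Milder assumptions, in subjects.** With 5-30% negative on Day 1, 20-40% of these emerging on placebo, and the drug cutting that by 20-40%, late entrants are 1.0-14.6% of the placebo set. The favipiravir set is about 0.6 to 13 subjects smaller, out of 275 randomised per arm. With no drug effect on PCR the difference is zero.

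**4. Effect on the estimate.** Two simulation models were used, both on assumed inputs.

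- *Fixed emergence probabilities as in step 2* (60,000 per arm, Cox HR). At p = 0.60 the HR moves up, from about 1.66 to 1.72; at p = 0.80 it rises by 0.01-0.03. At p = 0.941 it goes from 1.717 to 1.720-1.726.
- *Viral-load decline with assay noise* (275 per arm, 300 runs per scenario, Gehan-Wilcoxon test, 58-80% Day 1 positive). With an effective drug, Day-1-only inclusion was balanced. Day 1-3 inclusion was about 1-4 percentage points lower on favipiravir (for example 64.0% v 67.7%). Going from the Day 1 set to the Day 1-3 set, the HR moves down: 1.67 to 1.61, and 2.22 to 2.10. With no drug effect, inclusion was essentially equal between arms and rejection rates were 3.7-5.7%, consistent with 5%.

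The signs differ for an understandable reason. In the first model, late entrants add event-free time, mostly to placebo. In the second they tend to be low-load subjects who clear soon after, and there are more of them on placebo.

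**5. Scale.** The standard error of log HR at 112 events is about 2/√112 = 0.189. The shift 1.66 to 1.72 is ln(1.72/1.66)/0.189 = 0.19 SE. The shift 2.22 to 2.10 is ln(2.22/2.10)/0.189 = 0.29 SE.

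**The case against.** The strongest reply is that this hardly matters, and much of that stands. Day-1-positive subjects are included whatever follows, so only a minority is touched. Near the one related figure in the documents (94.1%), the shift is negligible. If the drug has no effect on PCR, selection does not differ by arm. The exploratory conversion endpoint assessed from Day 3 onward largely removes the unequal early event-free time, though not the selection. SAP 3.1 may already hold a Day-1-positive analysis.

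Three stronger readings may tempt a reader. The documents do not support them.

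- **That the rule inflates the favipiravir effect.** The sign is a product of the model: one raises the HR, the other lowers it.
- **That 550 subjects for 112 events shows positives are scarce, so late entry is common.** On the Section 10.2.4 medians and 10 days, event probabilities are 1 − 2^(−10/5) = 0.75 and 1 − 2^(−10/2.9) = 0.908, averaging 0.829. So 112 events need about 135 evaluable subjects, 25% of 550. The plan does not explain the gap. The assumed emergence rates alone would make 35-42% evaluable even if nobody were positive on Day 1, so the inference contradicts them.
- **That a confirmatory claim is at risk.** Viral shedding is headed key secondary, but the testing order in Section 10.6 contains only clinical recovery, broad progression and narrow progression.

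A defence that the wider rule is needed to reach the event count is weak. Section 9.2.1 ties enrolment to events: "Until the sub-study enrollment is completed (112 events have been counted), all subjects will be enrolled into the viral shedding sub-study". Other sections plan about 550 subjects, so if that number is treated as fixed, restriction costs some precision.

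**Conclusion.** The point holds as a modest design weakness. The rule lets post-dose results decide entry for subjects negative or missing on Day 1, and gives those subjects event-free time by construction. When the drug works, the analysed groups are not purely the randomised ones.

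The likely effect is small and of unknown sign: about 0.1 on the HR at most (0.12 for 2.22 to 2.10), under about 0.3 SE at 112 events. This rests on assumed Day 1 positivity of roughly 60-94% and on assumed emergence or viral-load decline. It concerns the credibility of the viral estimate and not type I error under no PCR effect. The change is worth making because it is cheap and removes an avoidable question about the result.

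**What to change.** Before unblinding:

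1. Define the main viral-shedding set as subjects with detectable RNA in the Day 1 saliva sample.
2. State that this sample precedes dose 1. Section 13.0 describes version 3.0 as the last version implemented, so collection may be finished; if so, confirm the order from sample and dose records.
3. Keep the Day 1-3 set as a sensitivity analysis.
4. Report by arm how many subjects enter each set, and how many were negative or missing on Day 1.
5. Apply the same rule to the culture endpoint.

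If SAP 3.1 already contains a Day-1-positive analysis, make it the main one.

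The cost is SAP wording and a records check. Late-positive subjects and those without a Day 1 sample leave the main set, with a small loss of precision if enrolment is fixed at about 550. The 112-event target does not change.
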